9.3.4 Assessment of Study Objectives

The primary study aim ([1.1.1](#)) will be assessed by a one-sided continuity-corrected test of proportions with pooled variance to compare the response rates after 6 cycles in the two regimens, and the futility and efficacy monitoring rules ([Section 9.3.3](#)). The response rate by the end of 6 cycles will be calculated on each regimen, including placement of a 95% confidence interval. If a patient is a responder and later has PD or goes off protocol therapy, then the patient will be counted as a responder. If the response rate on Regimen B is significantly better, then it will be considered a therapeutic regimen worthy of further testing in patients with newly-diagnosed high-risk neuroblastoma. In addition, the response rate by the end of 6 cycles (based on confirmed responses) will also be calculated for each regimen, with responders defined as patients who achieve a confirmed minor response or better per the revised INRC⁶⁸ as their best overall response by the end of 6 cycles as determined by central review.

To address secondary objective [1.2.1](#), Kaplan-Meier curves of PFS and OS will be generated by regimen and compared using log-rank tests. PFS and OS will also be evaluated separately in the cohorts of patients enrolled prior to and post-Amendment 4 given the reduction in maximum cycles of therapy from 17 to 6 cycles.

To assess secondary aim [1.2.2](#), toxicities (Grade ≥ 3) experienced on Regimen B will be descriptively summarized.

Exploratory aim [1.3.1](#) will be assessed by exploring the relationship between response (responder vs. non-responder) after 6 cycles on Regimen B with serum cytokine levels (IL1, IL6, TNF-alpha, IFN-gamma, etc.), tumor resident immune cells (NK cells, TAMS, TILS), and critical immune cell suppressing proteins (B7H3, PDL-1) using Fisher's exact test for categorical and Wilcoxon rank-sum test for continuous factors.

To address exploratory objective [1.3.2](#), GD2 levels in tumor cells from bone marrow samples will be correlated with response (responder vs. non-responder) after 6 cycles using Fisher's exact test for categorical and the Wilcoxon rank-sum test for continuous factors.

To assess exploratory aim [1.3.3](#), the occurrence of pain on each regimen as reported by patient report and opiate use will be descriptively summarized. Descriptive and summary statistics will be used to describe the scores from the Faces Pain Scale-Revised during the dinutuximab infusion and on Day 1 with irinotecan and temozolomide alone for each arm separately. Confidence intervals will be constructed for the mean and frequency estimates. The Day 1 patient reported outcome data are expected to be similar between the 2 regimens, while differences during or after completion of treatment may be observed.

9.4 **Evaluability for Response**

All eligible patients will be considered evaluable for response.

9.5 **Evaluability for Toxicity**

All eligible patients will be evaluable for toxicity from the time of their first treatment with eflornithine, irinotecan, temozolomide, or dinutuximab.

The study committee will review ototoxicity data closely during monthly committee meetings. If a difference in the incidence of hearing loss of $>15\%$ in eligible patients treated on the interrupted schedule enacted with Amendment 2A is detected among patients on the DFMO-containing Regimen B as compared to Regimen A, the study committee will notify the DSMC and CTEP and discuss potentially suspending accrual and further modifying the DFMO dose and/or schedule. In this context, hearing loss is defined as “an increase of 15dB or more from baseline in hearing threshold at two contiguous frequencies between 500-3000Hz” as this is the criterion for which DFMO is held for hearing loss.

9.6 **Gender and Minority Accrual Estimates**

The gender and minority distribution of the study population is expected to be:

DOMESTIC PLANNED ENROLLMENT REPORT								
Racial Categories	Ethnic Categories						Total	
	Not Hispanic or Latino		Hispanic or Latino					
	Female	Male	Female	Male				

American Indian/ Alaska Native	0	0	0	0	0
Asian	0	3	0	0	3
Native Hawaiian or Other Pacific Islander	0	0	0	0	0
Black or African American	8	5	0	0	13
White	18	29	5	10	62
More Than One Race	0	0	0	0	0
Total	26	37	5	10	78

INTERNATIONAL (including Canadian participants) PLANNED ENROLLMENT REPORT						
Racial Categories	Ethnic Categories				Total	
	Not Hispanic or Latino		Hispanic or Latino			
	Female	Male	Female	Male		
American Indian/ Alaska Native	0	0	0	0	0	
Asian	0	2	0	0	2	
Native Hawaiian or Other Pacific Islander	1	1	0	0	2	
Black or African American	0	0	0	0	0	
White	4	7	2	0	13	
More Than One Race	0	0	0	0	0	
Total	5	10	2	0	17	

This distribution was derived from ANBL1221.

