1.2 Secondary Aims

1.2.1 To compare progression-free survival and overall survival between patients receiving dinutuximab, irinotecan and temozolomide with and without the addition of DFMO.

1.2.2 To define the toxicity profile of DFMO administered with dinutuximab, irinotecan and temozolomide.

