3.1.6 Patient Stratification

Patients will be randomized 1:1 to Regimen A (irinotecan/temozolomide/dinutuximab) or Regimen B (DFMO + irinotecan/temozolomide/dinutuximab), with stratification according to the following 4 factors:

- Disease category (measurable vs. evaluable)
- Prior anti-GD2 therapy (prior exposure to anti-GD2 antibody vs. no prior exposure to anti-GD2 antibody)
- Prior DFMO therapy (prior exposure to DFMO vs. no prior exposure to DFMO)
- MYCN status (amplified vs. non-amplified vs. unknown)

Please refer to [Appendix II](#) for a flowchart for determining the appropriate stratum.

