9.0 STATISTICAL CONSIDERATIONS

9.1 Sample Size and Study Duration

The proposed randomized Phase 2 study will require enrollment of 90 eligible patients, 45 assigned to each regimen. Enrollment may proceed up to 95 patients to allow up to 5% potentially ineligible patients.

Expected accrual for this study would be similar to the accrual rate of 42 patients/year observed on the ANBL1221 expansion cohort at non-Australian and New Zealand sites as the patient population and eligibility are very similar. We anticipate that given the positive results of ANBL1221 and the reality that this backbone has become widely used for first relapse, there should be similar accrual rates for this trial. Assuming this rate, the trial would take about 2.3 years to complete accrual of up to 95 patients. The study will require an additional 12 months for completion of therapy and toxicity evaluation for a total study duration of approximately 3.3 years.

The sample size may be increased if accrual is fast: specifically, if 30 months after the study commencement the average accrual rate over the previous 3 months is above an annual rate of 41 patients per year, then the study may be amended (blindly to the interim outcome data) and accrual increased to 148 eligible patients. In this case, enrollment may proceed up to 155 patients to allow up to 5% potentially ineligible patients. Assuming an accrual rate of 42 patients/year (this rate would be amended if needed based on observed accrual rate), the trial would take about 3.7 years to complete accrual and a total study duration of ~4.7 years. The amendment would be submitted after the 30-month time point so that the study will not need to be closed to accrual as a result of the increase in the target accrual.

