9.2 Study Design

This will be a prospective, randomized phase 2 trial to determine whether the addition of DFMO to the dinutuximab/irinotecan/temozolomide backbone improves the response rate compared to the backbone alone. Patients will be randomized 1:1 to Regimen A (irinotecan/temozolomide/dinutuximab) or Regimen B (DFMO + irinotecan/temozolomide/ dinutuximab), stratified by disease category (measurable vs. evaluable), prior anti-GD2 therapy (prior exposure to anti-GD2 antibody vs. no prior exposure to anti-GD2 antibody), prior DFMO therapy (prior exposure to DFMO vs. no prior exposure to DFMO), and *MYCN* status (amplified vs. non-amplified vs. unknown). We will monitor for differences in the response rate between the two regimens for early indication of futility and efficacy.

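### The all-patient PFS and OS comparison has no stratified test and no hazard ratio with a confidence interval, although randomization is stratified on four factors

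*Combined protocol and SAP*

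**What the plan says.** Aim 1.2.1 in section 1.2 is "To compare progression-free survival and overall survival between patients receiving dinutuximab, irinotecan and temozolomide with and without the addition of DFMO". The analysis is given in two sentences of section 9.3.4. The first, with no restriction to any cohort, says that "Kaplan-Meier curves of PFS and OS will be generated by regimen and compared using log-rank tests". The second says that "PFS and OS will also be evaluated separately in the cohorts of patients enrolled prior to and post-Amendment 4", the reason being "given the reduction in maximum cycles of therapy from 17 to 6 cycles".

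Section 3.1.6 randomizes 1:1 "with stratification according to the following 4 factors": disease category, prior anti-GD2 therapy, prior DFMO and MYCN status. The first three have two levels and MYCN status has three. Section 9.2 repeats this.

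Nothing says that the log-rank tests use these factors. No hazard ratio, Cox model or confidence interval for the PFS or OS treatment effect appears anywhere. No significance level, sidedness or power is given for PFS or OS. By contrast, section 9.3.4 plans 95% intervals for the response rates and intervals for the pain summaries.

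**The concern.** Two things are missing from the all-patient comparison.

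- **An effect size with its precision.** Kaplan-Meier curves and a log-rank p-value do not say how large the difference between regimens is or how uncertain it is. Sections 1.1 and 2.7 look ahead to frontline testing, and planning that work needs an effect estimate. This gap does not depend on any modelling assumption.
- **A link between randomization and analysis.** Stratified allocation balances the regimens on the chosen factors. If those factors predict PFS or OS and the test ignores them, the variance it uses is too large for the balanced design. The test then rejects less often than its nominal level, and an unadjusted hazard ratio lies closer to 1 than the one within strata. Section 2.1 itself describes MYCN amplification as marking a worse prognosis. Silence also leaves the choice between a plain and a stratified test open until the data are seen.

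**Working it through.** **The plan's own figure.** Section 9.1 "will require enrollment of 90 eligible patients, 45 assigned to each regimen". Inputs from section 9.3.1.1: 40% vs 60%, one-sided 20%, power 80%, continuity-corrected, so both normal quantiles are 0.8416.

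- Uncorrected: n0 = [0.8416 x sqrt(2 x 0.5 x 0.5) + 0.8416 x sqrt(0.24 + 0.24)]^2 / 0.20^2 = 34.7.
- Corrected: n = (n0/4) x [1 + sqrt(1 + 4/(n0 x 0.20))]^2 = 44.1, so 45 per regimen and 90 in all.

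The figure reproduces, but it concerns response. There is no PFS or OS design figure to reproduce.

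**Strata.** 2 x 2 x 2 x 3 = 24 cells, or 90/24 = 3.75 patients per cell. MYCN status by prior anti-GD2 gives 3 x 2 = 6 strata, averaging 15 patients.

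**Simulation of plain vs 6-stratum log-rank.** From the documents: 90 patients, 1:1, four factors. Assumed:

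- permuted blocks of 4 within the 24 cells
- exponential PFS with a median of 12 months, and uniform censoring at 12-48 months
- MYCN 30% amplified, 60% non-amplified, 10% unknown; prior anti-GD2 60%; measurable disease 50%; prior DFMO 10%
- a 60/40 split at Amendment 4
- true hazard ratio 0.65, test at one-sided 10%

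The prognostic hazard ratios for MYCN, anti-GD2 and cohort are 2, 1.5 and 1.3 (moderate) or 3, 2 and 1.5 (strong). Each scenario has 6,000 replicates. The estimate is exp[(O-E)/V]. Ranges cover two runs: unknown MYCN carrying the non-amplified risk, or a risk midway on the log scale.

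| Factors | Level, plain | Level, stratified | Power, plain | Power, stratified | HR, plain | HR, stratified |
|---|---|---|---|---|---|---|
| None | 10.4-11.0% | 10.8-11.3% | 67% | 64-65% | 0.64 | 0.64-0.65 |
| Moderate | 9.0-9.4% | 9.5-10.2% | 62-63% | 63-64% | 0.67 | 0.65 |
| Strong | 8.1-8.2% | 9.4-10.6% | 57% | 62% | 0.69 | 0.65 |

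The Monte Carlo standard error of a level is sqrt(0.1 x 0.9/6000), about 0.4 points.

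**Why not all 24 cells.** A second setup used a two-sided 5% level, a hazard ratio of 0.6 and other assumed prevalences and effects. Power for the plain vs 24-cell test was 57% vs 46% with no prognostic effect, 48% vs 46% moderate, 39% vs 43% strong and 27% vs 41% very strong. Stratifying by MYCN status alone gave 55%, 50%, 44% and 36%. The plain test's level in the same order was 5.4%, 3.7%, 3.1% and 2.2%.

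**Precision of a hazard ratio.** The 95% limits are the estimate divided and multiplied by exp(1.96 x 2/sqrt(d)) for d events. That factor is 1.55 for d = 80 and 1.79 for d = 45. If 70 events split 42 and 28 between the cohorts, it is 1.83 and 2.10.

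**The case against.** Four objections carry weight.

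1. A reader might infer that PFS and OS are compared only within the two Amendment 4 cohorts. The text does not support that. The first sentence of 9.3.4 covers all patients, and the second adds the cohort evaluations with the word 'also'. Allocation is 1:1 throughout, so cohort does not confound the all-patient comparison.
2. A reader might infer that the planned test certainly runs below its nominal level. That cannot be shown. The absence of stratification is read from silence, no level is stated for PFS or OS, and the documents do not quantify how prognostic the factors are. With no prognostic effect the plain test is not conservative and has slightly more power. Where it is conservative, it does not add false positives.
3. The shift from 0.65 to 0.69 is partly a change of estimand, since marginal and within-stratum hazard ratios differ. It is not an error in a planned estimate, because no hazard ratio is planned.
4. PFS and OS are secondary, and 9.3.4 ties the decision on further testing to response. Kaplan-Meier curves will also be shown, so readers will have more than a p-value.

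All four stand, and they keep the point small. They do not supply the missing effect estimate, nor do they settle which log-rank test will be used.

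Replacing the cohort evaluations with a regimen-by-cohort interaction test would not be an improvement. With 42 and 28 events its standard error is sqrt(4/42 + 4/28) = 0.49, so a twofold ratio of hazard ratios would be detected only about 30% of the time at two-sided 5%.

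**Conclusion.** The point holds as a modest, inexpensive improvement to a secondary analysis. That no hazard ratio with interval is planned, and that no stratification is named, can be read directly from section 9.3.4.

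The statistical cost of ignoring the strata is conditional. If MYCN status and prior anti-GD2 therapy are moderately to strongly prognostic, the plain test's level is about 8-10% against a nominal 10%, its estimate is about 0.67-0.69 against 0.65, and stratifying gains about 1-5 points of power. If neither is prognostic, stratifying costs about 3 points. These sizes rest on the assumed event rates, prevalences, factor effects and block method. The one-sided 10% level is also assumed. The simulation used a one-step hazard ratio and did not fit the Cox model.

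The response analysis, its 90 patients and the interim rules are untouched.

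**What to change.** In section 9.3.4:

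- Make the main all-patient comparison of PFS and of OS a log-rank test stratified by MYCN status and prior anti-GD2 therapy (6 strata, not 24 cells). State its level and sidedness.
- Report the hazard ratio with 95% confidence interval from the Cox model stratified the same way.
- Keep the plain log-rank as a sensitivity analysis.
- Keep the Amendment 4 cohort evaluations and give a hazard ratio with interval for each. A regimen-by-cohort interaction estimate may be added descriptively but should not replace them.

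This is a change of wording only, because the factors are already recorded for randomization. It should be settled before PFS and OS are compared by regimen. The price is about 3 points of power if neither factor is prognostic. Choosing these two of the four factors is a judgement: the background section supports MYCN status, while the documents do not quantify the prognostic weight of prior anti-GD2 therapy.

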2.5 Dosing Rationale

In this trial, DFMO will be dosed orally. The bioavailability of orally administered DFMO ranges from 50-60% in multiple studies.²⁶ The dose of DFMO to be used for this trial (6,750 mg/m²/day divided 3 times a day orally) was the recommended phase 2 dose determined on the NANT consortium N2012-01 trial of DFMO in combination with cyclophosphamide, topotecan and celecoxib. The half-life of DFMO is 3-4 hours when delivered orally, therefore, a TID dosing regimen provides continuously higher plasma concentrations to optimize systemic polyamine depletion. DFMO will be given at this dose during therapy.

Starting with Amendment 2A, DFMO will be given on a discontinuous basis, allowing for a 7-day break without DFMO administration in each cycle, similar to the dosing used in the NANT N2012-01 trial. Four of the first eight patients enrolled on the DFMO containing arm (Regimen B) of this study with available ototoxicity data developed documented Grade 3 hearing loss from their baseline. Hearing loss is a known toxicity of DFMO and is typically reversible. Prior studies have shown that the risk of DFMO-associated ototoxicity is decreased when the DFMO is administered in an intermittent fashion, with a 7-14 day break per cycle. At similar or higher dosing compared to that used in ANBL1821, the incidence of Grade 3 or higher hearing loss with interrupted dosing was less than 5%^{40, 30, 29} Similarly, in the NANT2012-01 trial, DFMO dosed at 3000-9000 mg/m²/day for 21 days out of a 28-day cycle resulted in only 1 of 24 patients experiencing new Grade 3 hearing loss. This hearing loss was reversible and did not recur with re-treatment.³⁹ The NANT2012-01 trial was conducted in a relapsed NBL population similar to that of ANBL1821 supporting that intermittent dosing of

DFMO may decrease the risk for significant ototoxicity. Therefore, given the incidence of hearing loss seen initially on this study with continuous dosing, this trial will now include a 7-day break in DFMO dosing to decrease the chances of additional hearing loss. Additionally, DFMO will be held at first detection of significant hearing loss.

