9.3.3 Monitoring for Futility or Efficacy of Regimen B

Monitoring for futility or efficacy of the DFMO arm will be performed. There would be cause to stop the trial early if the response rate on Regimen B appears to be insufficiently efficacious or superior to Regimen A. The response rates will be monitored after 2 cycles to decrease the amount of time the study must be closed for interim analysis. ANBL1221 data showed that most patients that responded on

the I/T/DIN arm did so early, with 16 of the 22 patients with confirmed responses demonstrating partial response or better after the first 2 cycles. With Amendment 4, the interim analysis will be done using overall response, or if overall response was coded as Not Done due to a missing component of the disease evaluation, the response at soft tissue and bone sites will be used as the overall response at the end of Cycle 2.

Futility monitoring will be performed per Ellenberg and Eisenberger (1985):⁶⁹ if at half the sample size the observed response rate after 2 cycles for Regimen B is less than that for Regimen A, accrual will be halted and the DSMC will consider permanently stopping accrual. Due to the potential for a drug supply issue, the futility analysis will be performed sooner, after accrual of 40 patients rather than at half the sample size of 45 patients. The futility rule will be executed once, using data from the first 40 eligible patients enrolled. This two-stage rule has been shown to lead to a reduction in the expected sample size if Regimen B is ineffective, with minimal loss in power.⁷⁰

A one-sided O'Brien-Fleming group-sequential boundary will be used to monitor for efficacy of Regimen B if the sample size is increased to 148 eligible patients. Interim monitoring will be performed at 50% of the expected information (N=74, 37 eligible patients per regimen), and 100% information. The critical p-values (upper boundary z-score) for the interim looks (maintaining an overall significance level of 20%) are 0.0699 (1.4763) at the first look, with the final analysis performed at a significance level of 0.1803 (0.9141).

If the futility and efficacy monitoring rules are not triggered, accrual will continue as planned, and the one-sided continuity-corrected test of proportions with pooled variance will be applied.

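### The planned Regimen B summary of Grade 3 or higher toxicity does not separate the two DFMO schedules, so its hearing-loss rate would describe neither schedule

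*Combined protocol and SAP*

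**What the plan says.** Section 2.5 (Dosing Rationale) sets out the change: "Starting with Amendment 2A, DFMO will be given on a discontinuous basis, allowing for a 7-day break without DFMO administration in each cycle". The reason concerns "Four of the first eight patients enrolled on the DFMO containing arm (Regimen B) of this study with available ototoxicity data", who had documented Grade 3 hearing loss from baseline. The break was introduced "given the incidence of hearing loss seen initially on this study with continuous dosing". For comparison, the section says of earlier studies at similar or higher doses that "the incidence of Grade 3 or higher hearing loss with interrupted dosing was less than 5" per cent. It also cites 1 of 24 patients in an earlier neuroblastoma trial that gave DFMO on 21 of 28 days.

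Section 9.3.4 (Assessment of Study Objectives) gives the analysis for aim 1.2.2, the toxicity profile, in one line: "toxicities (Grade ≥ 3) experienced on Regimen B will be descriptively summarized". It says nothing about schedule.

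Section 9.5 (Evaluability for Toxicity) does recognise the schedules. Its trigger, a difference of more than 15% in hearing loss between Regimen B and Regimen A, is confined to "eligible patients treated on the interrupted schedule enacted with Amendment 2A". That rule governs when the study committee notifies the DSMC and CTEP. It uses a threshold shift of at least 15 dB at two contiguous frequencies, not CTCAE grade.

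**The concern.** Aim 1.2.2 is meant to define the toxicity of DFMO added to the backbone. Hearing loss is the toxicity that made the sponsor change the schedule, so it is the one most likely to differ between patients treated before and after the change. If every Regimen B patient goes into one summary, the hearing-loss figure is a weighted average of two exposures. Its weights are set by how many patients happened to enrol before Amendment 2A.

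Anyone using the result to plan later work would read that average as the toxicity of Regimen B as the protocol now defines it. The final analysis would also drop a distinction that the plan already draws for monitoring.

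**Working it through.** **Is there a plan figure to reproduce?** The plan states no expected hearing-loss rate. The denominator used below is the planned 45 eligible patients per arm in Section 9.3.1.1. That figure reproduces: 40% against 60%, one-sided 20% type I error, continuity-corrected with pooled variance, needs 45 per arm, with power 80.6% by the normal formula.

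**How different are the schedules?** Days of DFMO over six cycles, counting the 7-day lead-in:
- Continuous: 28 + 5 × 21 = 133 days.
- Interrupted (Sections 4.6.3 and 4.7.3): 21 + 5 × 14 = 91 days.
- Reduction: (133 − 91)/133 = 32%.

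**Inputs for the pooled rate**
- Continuous dosing, Grade 3 hearing loss: 4/8 = 50%, exact (Clopper-Pearson) 95% interval 15.7% to 84.3% (Section 2.5).
- Interrupted dosing: 5%, taken from the upper limit that Section 2.5 cites from other studies. This is an assumption for this trial.
- Number on continuous dosing, k: at least 8. The total is not stated, so 8 is the minimum, and it assumes that these patients were eligible.

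**Formula.** Pooled rate = [k × p(continuous) + (45 − k) × p(interrupted)]/45.

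**At k = 8 and 5% on interrupted dosing**
- Point estimate: (8 × 0.50 + 37 × 0.05)/45 = 5.85/45 = 13.0%, which is 2.6 times 5%.
- Lower limit for 4/8: (8 × 0.157 + 37 × 0.05)/45 = 6.9%, 1.4 times.
- Upper limit for 4/8: (8 × 0.843 + 37 × 0.05)/45 = 19.1%, 3.8 times.

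**Sensitivity to the assumptions** (continuous rate held at 50%)

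| k | Interrupted rate | Pooled rate |
|---|---|---|
| 8 | 1/24 = 4.2% | 12.3% |
| 8 | 10% | 17.1% |
| 8 | 15% | 21.2% |
| 10 | 5% | 15% |
| 15 | 5% | 20% |
| 20 | 5% | 25% |

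The pooled rate exceeds the interrupted rate in every row. The ratio narrows as the interrupted rate rises (17.1/10 = 1.7; 21.2/15 = 1.4) and would be 1 if the two schedules carried the same risk.

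**Does the same mixing matter for response?** Suppose the interrupted schedule gives 60% and the continuous schedule differs by 20 points in either direction. At k = 8:
- Continuous 40%: (8 × 0.40 + 37 × 0.60)/45 = 56.4%.
- Continuous 80%: (8 × 0.80 + 37 × 0.60)/45 = 63.6%.

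The shift is about 4 points. At an assumed k = 20 it would be about 9 points (51.1% to 68.9%).

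**Power of a response comparison from Amendment 2A onward** (40% against 60%, same test, equal exclusions in both arms): 74.5% at k = 8 (37 per arm), 72.7% at k = 10, 67.7% at k = 15 and 61.6% at k = 20.

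**The case against.** **Hearing loss by schedule is already followed.** Section 9.5 requires monthly ototoxicity review and a comparison with Regimen A limited to the interrupted schedule. This stands as far as it goes, and it shows that the data will exist. It is a monitoring rule with its own hearing definition, however, and nothing carries it into the aim 1.2.2 report. Nor does Section 9.3.4 forbid a split; it simply does not plan one.

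**The size is uncertain.** This stands. The 4/8 is a small early cluster that prompted the change, among patients with data available, so it may run high. The 5% comes from other studies. A reader might take 2.6-fold as a firm figure, but the interval on 4/8 alone widens it to 1.4 to 3.8.

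Three stronger readings are tempting, and the documents do not support them.

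- *The response comparison fails to describe the regimen.* The intent-to-treat test remains a valid randomised comparison. At the documented minimum, 37 of 45 Regimen B patients (82%) are on the interrupted schedule, and no evidence is given that response differs by schedule. The separate Amendment 4 analysis ("PFS and OS will also be evaluated separately in the cohorts of patients enrolled prior to and post-Amendment 4") is no precedent, because its stated reason is the fall from 17 to 6 maximum cycles, whereas response is assessed by the end of Cycle 6.
- *The futility look is undermined.* It is made "using data from the first 40 eligible patients enrolled". If all eight patients were eligible and the arms even, they would be 8 of 20 on Regimen B (40%). It is still a randomised comparison, and a trigger halts accrual for DSMC consideration, not automatic permanent closure.
- *Only the interrupted schedule would go forward.* The treatment sections now give only that schedule, but Section 9.3.4 names Regimen B alone, and Section 9.5 leaves further dose or schedule changes open.

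**Conclusion.** The point holds for the toxicity report. As written, Section 9.3.4 would produce a Regimen B hearing-loss rate that belongs to neither schedule and probably overstates the rate on the schedule now in the protocol.

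At the documented minimum of 8 continuous-schedule patients among 45, and an assumed 5% on interrupted dosing, the pooled rate is about 13%, with a range of 6.9% to 19.1% from the interval on 4/8. More continuous-schedule patients would raise it. The direction rests on interrupted dosing carrying the lower risk in this trial, which the plan expects but the documents do not yet show.

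The primary response analysis needs no change on this ground. No view is taken on which schedule is right.

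**What to change.** In Section 9.3.4, under aim 1.2.2:

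1. Summarise Regimen B Grade 3 or higher toxicities, and hearing loss by the Section 9.5 definition, separately for patients enrolled before Amendment 2A and from Amendment 2A onward.
2. State the number of patients in each group.
3. State how patients who were on study at the change and switched schedule are classified. Sections 4.6.3 and 4.7.3 give only the interrupted schedule, with no branch for earlier enrolees, so some may have switched.

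Keep the pooled intent-to-treat response test as primary. A response estimate in patients randomised from Amendment 2A, against Regimen A patients randomised over the same period, is optional. With power of about 75% or less it should be labelled descriptive and should not compete with the primary result.

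The cost is a few sentences and one further table from data already collected. The subgroups are smaller, so their intervals will be wide. The contrast between them is by calendar time, not by randomisation, and should be presented as description.
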